6.4 Biomarker Analysis (Optional)

The purpose of this exploratory study is to assess the presence, type, and frequency of AML-related molecular mutations in this patient population and whether there is an association between specific mutations and disease outcome with the study therapy.

The planned biomarker analyses involve the analysis of protein and nucleic acids (i.e., RNA and/or DNA). Biomarkers deemed relevant to gain further knowledge about the pathomechanism of the disease or about the drug (i.e., mode of action or safety of the drug) may be measured, based on newly emerging data from other ongoing trials of these investigational drugs and/or literature data. However, the study sponsor reserves the right not to conduct all or part of the biomarker analysis. Data from this biomarker analysis may be correlated with various other data obtained in this study (e.g., clinical efficacy, pharmacokinetics, toxicity).

Peripheral blood samples and/or aspirate bone marrow samples will be collected and stored for potential molecular studies at screening, between day 21 and day 26 of every even cycle and at End of Treatment visit.

Specimens to study AML-related molecular mutations will be collected from patients who give specific consent to participate in this optional research. The Informed Consent Form will contain a separate section that addresses participation in the molecular mutation assessments. The Investigator or authorized designee will explain to each patient the objectives, methods and potential hazards of participation in this research. Patients will be told that they are free to refuse to participate and may withdraw their specimens at any time for any reason during the storage period. A separate, specific signature will be required to document a patient's agreement for this purpose.

Dates of consent should be recorded in the associate page of eCRF. For sampling procedures, storage conditions, and shipment instructions, see the laboratory manual.

Collection and submission of these samples is contingent upon the review and approval of the exploratory research portion of the Informed Consent Form by each site's Institutional Review Board or Ethics Committee and, if applicable, appropriate regulatory body. If a site is not granted approval for these assessments, this section of the protocol will not be applicable at that site.

6.5 Efficacy Endpoints

6.5.1 Primary Endpoint

The primary efficacy endpoint is the overall survival (OS) measured as the time from randomization until death from any cause.

6.5.2 Secondary Endpoints

6.5.2.1 Morphologic Complete Remission (CR) rate

6.5.2.2 *The CR rate is the proportion of patients who achieve a morphologic CR according to the IWG response criteria ([Appendix F](#)) in the absence of interceding therapies, including salvage treatments and HSCT, within the study period. Transfusion Independence (TI)*

Transfusion independence rate is defined as the proportion of patients who achieve eight weeks or longer with neither red blood cell (RBC) nor platelet (PLT) transfusions during the study period [[Fenaux, 2009](#); [Silverman, 2006](#)].

6.5.2.3 Complete Remission without minimal residual disease (CR_{MRD}-) rate

The CR_{MRD}- rate is the proportion of patients who achieve a CR with MRD negativity by multi-color flow cytometry, according to the IWG response criteria ([Appendix F](#)) within the study period.

6.5.2.4 Cytogenetic Complete Remission (CR_c) rate

The CR_c rate is the proportion of patients who achieve a reversion to a normal karyotype at CR ([Appendix F](#)) within the study period. This endpoint applies only to patients with abnormal cytogenetics at enrollment.

6.5.3 Exploratory Endpoints

6.5.3.1 Composite Complete Remission (cCR) rate

Composite complete remission (cCR) rate is the proportion of patients who achieve either a disease response of CR, CR_i or MLFS (i.e., cCR = CR + CR_i + MLFS) within the study period, ([Appendix F](#)).

6.5.3.2 Relapse Free Survival (RFS)

RFS is defined as the time from the date of achievement of CR or CR_i until the date of relapse (progression) or death from any cause, whichever occurs first. RFS is only defined for patients who achieve a CR or CR_i.

6.5.3.3 Progression Free Survival (PFS)

PFS is defined as the time from the date of randomization until the date of relapse (progression) or death from any cause, whichever occurs first.

6.5.3.4 Duration of Morphologic Complete Remission

Duration of Morphologic Complete Remission is defined as the time from the date of achievement of CR until the date of relapse (progression). Duration of CR is only defined for patients who achieve CR.

6.5.3.5 *Duration of Composite Complete Remission*

Duration of cCR response is the time from the date of achievement of either CR, CRi or MLFS (F) until the date of relapse (progression). Duration of cCR is only defined for patients who achieve a cCR.

6.5.3.6 *Time to CR*

Time to CR is defined as the time from the date of randomization until the date of CR in the absence of interceding therapies, including salvage treatments and HSCT.

6.5.3.7 *Morphologic Complete Remission (CR) within 6 cycles rate*

Morphologic complete remission (CR) within 6 cycles rate is defined as the proportion of patients who achieve CR in the absence of interceding therapies, including salvage treatments and HSCT, within 6 treatment cycles.

6.5.3.8 *Quality of Life*

Computation of the global health status and of selected functional scales and symptom scales from the EORTC QLQ-C30 questionnaire will be performed and their change from baseline over the study period will constitute the endpoints.

6.6 **PK Endpoints**

- To characterize the pharmacokinetics (PK) of pracinostat and its main metabolites in AML patients by a population pharmacokinetic approach
- To characterize demographic, physiopathological and therapeutic covariates that may influence pracinostat PK parameters and their interindividual variability
- To characterize the pracinostat exposure-response relationship for safety and efficacy endpoints (PK/PD)
- To assess the possible drug interaction of Pracinostat on the PK of AZA in AML patients by comparing the descriptive statistics of PK parameters of azacitidine in the two groups

7 DISCONTINUATION FROM STUDY TREATMENT PHASE OF THE STUDY

7.1 Patient Treatment Discontinuation

If patients experience any of the following, then they must discontinue from the study treatment phase of the study:

- Documented disease progression or relapse after CR by the International Working Group (IWG) criteria ([Appendix F](#)).
- Lack of clinical benefit. Clinical responses may require at least 6 courses of study treatment. Therefore, discussion with the Medical Monitor is recommended prior to discontinuation of a patient on the basis of lack of clinical benefit.
- Irreversible or intolerable toxicity or abnormal and clinically significant laboratory findings that cannot be managed with study treatment dose reduction or interruption.
- A patient's request to discontinue treatment for any reason. If a patient requests discontinuation from study treatment due to an AE, the primary reason for discontinuation should be the adverse event.
- Non-compliance with study treatment or study-related assessments that compromise the proper evaluation of the patient's safety
- Lost to follow-up.
- Sponsor decision: The Sponsor reserves the right to discontinue the study at any time for either clinical or administrative reasons. This decision will impact patients in the treatment and in the Long-term Follow-up phases of the study.
- Pregnancy.

Upon study treatment discontinuation, assessments of the End of Treatment Visit must be completed (refer to Section [5.1.14](#)). Discontinued patients will enter the Long-term Follow-up phase of the study (refer to Section [5.2](#)). Every attempt must be made to contact the patient prior to assigning the patient a lost to follow-up status. For patients who are lost to follow-up, no Long-term Follow-up is expected.

7.2 Patient Withdrawal

Patients have the right to voluntarily withdraw from the study at any time and for any reason. In addition, a patient's participation in the study may be discontinued at any time at the discretion of the Investigator. Reasons for withdrawal from the study may include, but are not limited to, the following:

- Death
- Lost to Follow-Up
- Patient withdrawal of consent at any time during the patient's study participation, including during the Long-term Follow-up phase of the study.

Every effort should be made to obtain survival information on patients who withdraw from the study. The primary reason for withdrawal from the study should be documented

in the patient's study records and in the eCRF. Patients who withdraw from the study will not be replaced.

7.3 Site Discontinuation

The Sponsor has the right to close a site at any time. Reasons for closing a site may include, but are not limited to, the following:

- Non-compliance with ICH-GCP guidelines
- Inadequate rate of patient recruitment
- Poor protocol adherence
- Inaccurate or incomplete data recording
- No study activity (i.e., all patients have completed and all obligations have been fulfilled)

7.4 Study Termination

Study termination is defined as the time when all study treatments, study related-assessments, and study data collection are completed. Upon termination of the study, the Sponsor or designee will conduct site closure activities with the Investigator or site staff (as appropriate), in accordance with applicable regulations and the Study Manual.

The Sponsor reserves the right to temporarily suspend or terminate the study at any time for reasons including, but not limited to, safety issues or ethical reasons. The Sponsor or designee will also promptly inform the relevant regulatory authorities of the suspension/termination along with the reasons for such action, when applicable. Where required by applicable regulations, the Investigator or head of the medical institution must inform the Institutional Review Board (IRB)/Ethics Committee (EC).

8 SAFETY

8.1 Safety Parameters and Definitions

Safety assessments will consist of evaluating and recording AEs, including serious adverse events (SAEs); measurement of protocol-specified safety laboratory assessments; measurement of protocol-specified vital signs, ECGs, and physical examinations.

8.1.1 Definition of Adverse Events

An AE is any untoward medical occurrence associated with the use of a drug in humans, whether or not considered drug related. An AE (also referred to as an adverse experience) can be any unfavorable and unintended sign (e.g., an abnormal laboratory finding), symptom, or disease temporally associated with the use of a drug, and does not imply any judgment about causality. An AE can arise with any use of a drug (e.g., off-label use, use in combination with another drug) and with any route of administration, formulation, or dose, including an overdose.

Adverse reactions are defined as a subset of all adverse events for which there is reasonable possibility that the drug caused the event.

A preexisting medical condition should be recorded as an AE only if the frequency, severity, or character of the condition worsens during the study.

8.1.1.1 Suspected Adverse Reaction

Suspected adverse reactions are the subset of all AEs for which there is a reasonable possibility that the drug caused the event. For the purposes of US Investigational New Drug (IND) safety reporting, “reasonable possibility” means there is evidence to suggest a causal relationship between the drug and the AE. Suspected adverse reaction implies a lesser degree of certainty about causality than adverse reaction, which means any AE caused by a drug.

8.1.1.2 Life-threatening AE or Life-Threatening Suspected Adverse Reaction

An AE or suspected adverse reaction is considered “life-threatening” if, in the view of either the Investigator or Sponsor, its occurrence places the subject at immediate risk of death. It does not include an AE or suspected adverse reaction that, had it occurred in a more severe form, might have caused death.

8.1.1.3 Serious AE or Serious Suspected Adverse Reaction

An AE or suspected adverse reaction is considered “serious” if any of the following criteria is met:

- Death, including death that appear unrelated to the study treatment
- Life-threatening AE
- Inpatient hospitalization or prolongation of an existing hospitalization, excluding the following scenarios:
 - i. Emergency room visit or hospital visit without official admission

- ii. Prolongation due to management or progression of the underlying disease
 - iii. Hospitalization for a pre-existing condition, provided that any of the following criteria are met:
 1. The hospitalization was planned
 2. Hospitalization to accommodate study treatment administration or required study procedures
 3. Hospitalization due to disease progression
- Persistent or significant disability/incapacity
 - Congenital anomaly/birth defect
 - Important medical events that may not result in death, be life-threatening, or require hospitalization may be considered serious when, based upon appropriate medical judgment, they may jeopardize the patient and may require medical or surgical intervention to prevent one of the outcomes listed in this definition. Examples of such medical events include allergic bronchospasm requiring intensive treatment in an emergency room or at home, blood dyscrasias or convulsions that do not result in inpatient hospitalization, or the development of drug dependency or drug abuse.

8.1.1.4 *Unexpected AE or Unexpected Suspected Adverse Reaction*

An AE or suspected adverse reaction is considered “unexpected” if it is not reported in nature, severity or incidence in the current version of the pracinostat IB (Section 7. Appendix).

8.1.1.5 *Treatment-Emergent Adverse Event*

A TEAE is an adverse event that emerges, or a pre-existing adverse event that worsens in severity, any time after the patient receives Dose 1 of study drug (pracinostat/placebo) through the end of the AE reporting period. AEs with onset before the patient receives Dose 1 of study drug are considered as pre-treatment AEs. AEs with onset after the end of the reporting period (if any) are considered as post-treatment AEs.

Laboratory tests, vital signs, and ECG abnormalities will be reported as AEs only if the event is considered clinically significant or leads to medical intervention (e.g., additional concomitant medication or procedures, discontinuation of study drug). Refer to Section [8.2.5.3](#) for details.

8.2 Adverse Event Reporting

All adverse events occurring from the informed consent signature until 30 calendar days after last study drug (pracinostat/placebo) intake, or until the initiation of new therapy for AML, whichever occurs first, are to be recorded on the appropriate eCRF section.

Every effort must be made by the Investigator to categorize each adverse event according to its severity and its relationship to the study treatment (study drug and/or azacitidine).

All AEs will be followed until symptom resolution or until the condition stabilizes, unless, in the Investigator's opinion, the AE or laboratory abnormality/ies are not likely to improve because of the underlying disease or unless the patient is lost to follow-up.

Whenever a change in the severity of an AE (such as a worsening) has occurred, a follow up of the initial AE should be entered in the eCRF reporting the new severity.

Outcome of ongoing serious and non-serious AEs will be reported in eCRF until the end of the reporting period as above defined. All non-resolved serious and non-serious AEs beyond such date will be recorded in eCRF as "ongoing" without further follow-up.

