4.5 Dose Modifications and/or Dose Interruptions

Dose modifications are permitted to manage drug-related toxicities and to improve treatment tolerability in order to maintain the patient on therapy and prolong exposure to study treatment.

Dose modifications in Cycle 1 and Cycle 2 are discouraged to maximize exposure to study treatment and increase the likelihood of achieving an objective response.

Dose reduction is not allowed within each 28-day cycle, but only between cycles.

The Medical Monitor will review with the Investigator any decision to reduce, interrupt, or permanently discontinue either of the two components of the study treatment (pracinostat/placebo or azacitidine).

If a dose modification is required, a dose reduction should be implemented first, as described in the tables below.

One pracinostat dose reduction is allowed as shown in table below:

Table 1: Pracinostat Dose Reduction

| Dose Level | Pracinostat/Placebo |
|---------------|--|
| Starting Dose | One 60 mg capsule/3 days per week/ 3 weeks in every 28-day cycle |
| Dose Level -1 | One 45 mg capsule/3 days per week/ 3 weeks in every 28-day cycle |

Up to two AZA dose reductions are allowed as shown in the table below:

Table 2: AZA Dose Reductions

| Dose Level | Azacitidine |
|---------------|--|
| Starting Dose | 75 mg/m ² for 7 days of each 28-day cycle |
| Dose Level -1 | 37.5 mg/m ² (50%) for 7 days of each 28-day cycle |
| Dose Level -2 | 25 mg/m ² (33%) for 7 days of each 28-day cycle |

Prior to dose reduction, the Investigator must assess if the toxicity is thought to be due to pracinostat, based on the safety information provided in the Investigator Brochure, or AZA, based on the safety information provided in the AZA product labeling. Severe fatigue, anorexia, weight loss, diarrhea, vomiting and QT prolongation are adverse reactions likely related to pracinostat, whereas pyrexia, injection site reaction, constipation and renal toxicity are adverse reactions likely related to AZA. Myelosuppression (i.e., thrombocytopenia, anemia, leukopenia, and neutropenia) has been reported with similar frequency with pracinostat and AZA therapy.

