8.2.1 Serious Adverse Event (SAE)

Any SAE, irrespective of the relationship to study treatment, must be reported by the Investigator to CRO. Within 24 hours of the study site staff becoming aware of any SAE, the Investigator or the Investigator's designee must complete the eCRF with all necessary information. Any accompanying source documents (hospital records, autopsy report, etc.) should be faxed or e-mailed (as PDFs) at the following 24-hours contact information:

Email: [contact]

[contact]

SAEs should be collected from the informed consent signature until 30 calendar days after discontinuation or completion of study treatment, or until the initiation of new therapy for AML, whichever occurs first, and followed until resolution.

"Disease progression" or "relapse from remission" as such, should not be reported as SAEs.

"Death" is an outcome and should not be reported as an SAE, unless the cause leading to death is unknown. When recording an SAE with an outcome of death, the event or condition that caused or contributed to the fatal outcome should be recorded as the single serious adverse event term.

The Investigator must immediately (within 24 hours) report follow-up information for initial events to Clinipace and the Sponsor as described above. Follow-up information can include but is not limited to the following significant information:

- New signs or symptoms or a change in the diagnosis
- Clinically significant new diagnostic test results
- Change in causality based on new information
- Change in the event's outcome, including recovery
- Additional narrative information on the clinical course of the event

Investigators must also comply with local requirements for reporting of initial and follow-up SAEs to their Institutional Review Board (IRB)/ Ethics Committee (EC) according to their own interpretations of the regulations and their own institutional policies.

The Sponsor/ designee is responsible for SAE reporting to the Regulatory Authorities where the study is conducted, according to reporting requirements as per local regulatory rules.

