6.3 STUDY PERIODS

A patient is considered to have performed a cycle if during that cycle at least one dose of either AZA or PRAN/Placebo was administered to the patient, according to the Drug administration forms (Cycle x Day 1 drug administration /Pracinostat/placebo (for PRAN/PLAC) and drug administration – azacitidine forms (for azacitidine)).

A patient is to be considered entered in the long-term follow-up if:

1. Has at least one long-term follow-up visit filled (including the visit of End of Long-term Follow-up),

OR

2. Was discontinued from active treatment phase for reasons other than death, lost to follow-up, withdrawal by subject (*).

(*) Withdrawal by subject will be considered a criterion for not entering long-term follow-up only when it is reported in the eCRF as the reason for stopping both treatment and long-term follow-up phases and the dates of stop of treatment and long-term follow-up are equal.

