6.4 DATA DERIVATIONS AND DEFINITIONS

When reporting durations in months, divide the number of days by 30.4375; to report in weeks divide the number of days by 7; to report in years divide the number of days by 365.25. These algorithms for durations / time to event return decimal numbers, and ignore the actual numbers of days in the months or years between start date and stop date. The "year" used in these algorithms is 365.25 days long, and the "month" is one twelfth of that year.

Durations and time to events will be analyzed in days.

Baseline is defined as measurement obtained at the most recent assessment prior to the date of the first study treatment dose. Change from baseline will be calculated as the difference between the respective visit value and the baseline value.

Age will be calculated from the date of birth to Screening date.

For the calculation of exposure to study drug the Body Surface Area (BSA) is needed. If the baseline BSA is not documented, the next available documented BSA within the study period will be used for the calculation of the exposure.

The following will define pre-treatment use versus concomitant medication use:

- Prior use ending before receiving the first administration of study drug will be defined as "pre-treatment medications".
- Medications that started prior to the first administration of study drug, and continued pass through the first administered dose date as well as medication started after the first administered dose date will be defined as concomitant medications.

In a similar way, prior and concomitant procedures will be defined as:

- Prior procedures ending before receiving the first administration of study drug will be defined as "prior procedures".

- Procedures that started prior to the first administration of study drug, and continued pass through the first administered dose date as well as procedures started after the first administered dose date will be defined as concomitant procedures.

TEAEs will be considered as any event occurring, or a pre-existing event worsening, on or after receiving the first intake of pracinostat /placebo, and up to 30 days after receiving the last administration of study drug (date reported in the field Date of Last Pracinostat/Placebo Administration in the Subject Disposition page of the CRF will be used as the reference point).

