9.2.2 Treatment emergent adverse events (TEAEs)

Treatment-emergent AEs (TEAEs) are defined as AEs with onset date/time at or after the start date/time of the first intake of pracinostat /placebo, or AEs with onset date/time prior to start date/time of the first intake of pracinostat/placebo that worsen in severity after the start date/time of the first intake of pracinostat /placebo, up to the end of the observation period. The observation period is defined as 30 days after the last dose of pracinostat/placebo or start of a new therapy for AML, whichever occurs first. TEAEs will be summarized by treatment group.

Where dates and/or times are missing or partially missing, AEs will be considered treatment emergent, unless there is clear evidence (through comparison of partial dates and/or times) to suggest that the AE started prior or after the study period.

The following tables will be produced:

- An overview summary of TEAEs by treatment group, including counts and percentages of patients as well as the number of events. The summary includes the following kinds of AEs:
 - any TEAE;
 - TEAEs by worst NCI CTCAE grade (only number of patients and %)
 - TEAEs by NCI CTCAE grade
 - TEAEs causally related to study drug / AZA / study drug or AZA (i.e either component of the study treatment);
 - TEAEs leading to permanent discontinuation of study treatment;
 - TEAEs leading to interruption of study treatment (separately for study drug and AZA)
 - TEAEs leading to dose reduction
 - SAEs;
 - SAEs causally related to study drug / AZA / study drug or AZA;
 - fatal SAEs;
 - fatal SAEs causally related to study drug / AZA / study drug or AZA
 - TEAEs of special interest
 - TEAEs of special interest related to study drug
- The number and percentage of patients reporting TEAEs will be provided by treatment group, System Organ Class (SOC), Preferred Term (PT), worst NCI CTCAE grade, and total. TEAEs will be sorted by SOC and PT in alphabetical order (SOC and PT within SOC).
- The number and percentage of patients reporting TEAEs together with the number of AEs, will be provided by treatment group, SOC, PT, and total. Similar table will be provided including only ≥ 3 worst NCI CTCAE grade. TEAEs will be sorted by frequency (based on column Total of all AEs) of a SOC and the PTs within a SOC.
- The number and percentage of patients reporting study drug (pracinostat / placebo) related (as classified by investigator) TEAEs will be provided as described for “all

-

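### Adverse-event recording and TEAE status end 30 days after the last pracinostat/placebo capsule but SAE collection ends 30 days after study treatment, and the SAP has two rules on new AML therapy

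*Protocol*

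**What the plan says.** Protocol 3.1 separates two terms: study drug is pracinostat/placebo, and study treatment is study drug plus azacitidine. The safety windows use both.

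- **Adverse events.** Protocol 8.2 records them from consent "until 30 calendar days after last study drug (pracinostat/placebo) intake", or to the start of new AML therapy if that is earlier. Footnote U of the Schedule of Assessments and the adverse-event line of Protocol 5.1.14 use the same study-drug anchor.
- **Serious adverse events.** Protocol 8.2.1 collects them from consent "until 30 calendar days after discontinuation or completion of study treatment, or until the initiation of new therapy for AML, whichever occurs first".
- **Treatment-emergent events (TEAEs).** Protocol 8.1.1.5 runs to the end of the adverse-event reporting period, so it inherits the 8.2 limit. SAP 6.4 counts events "up to 30 days after receiving the last administration of study drug" and takes the date from the CRF field for the last pracinostat/placebo administration. SAP 9.2.2 states: "The observation period is defined as 30 days after the last dose of pracinostat/placebo or start of a new therapy for AML", whichever is first.
- **Later events.** SAP 9.2.1 calls them post-treatment and lists them. SAP 9.2.4 tabulates treatment-emergent serious events.

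Two passages bear on whether the drugs can part company. Protocol 4.5 has the Medical Monitor review "any decision to reduce, interrupt, or permanently discontinue either of the two components of the study treatment". SAP 6.3 treats a cycle as performed if "at least one dose of either AZA or PRAN/Placebo was administered to the patient".

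**The concern.** If a patient permanently stops the capsule but goes on with azacitidine, the adverse-event and TEAE windows close while protocol therapy is still being given. The serious-event window stays open. Three things follow on the literal text:

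- Non-serious events more than 30 days after the last capsule need not be recorded.
- Serious events in that time are collected but leave the TEAE-based tables, including those for serious events, fatal serious events and events of special interest.
- The azacitidine-related TEAE tables planned in SAP 9.2.2 rest on a window in which no azacitidine date appears.

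The second problem does not depend on azacitidine-only patients. SAP 6.4 and SAP 9.2.1/9.2.2 disagree on whether starting new AML therapy ends the TEAE window, so table counts depend on which section the programmer follows.

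**Working it through.** The plan gives no figure to reproduce. The check compares the windows and then counts days.

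**Windows side by side**

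| Place | Ends 30 days after | New AML therapy closes it? |
|---|---|---|
| Protocol 8.2, footnote U (AEs) | last pracinostat/placebo dose | yes |
| Protocol 5.1.14 (AE line) | last pracinostat/placebo dose | not stated there |
| Protocol 5.1.14 (visit timing) | end of treatment | visit brought forward if new treatment is urgent |
| Protocol 8.2.1 (SAEs) | end of study treatment (both drugs) | yes |
| SAP 6.4 (TEAEs) | last pracinostat/placebo dose | no |
| SAP 9.2.1 and 9.2.2 (TEAEs) | last pracinostat/placebo dose | yes |

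**Day count.** Day 1 is Day 1 of the last cycle with capsules.

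- Capsules are on Days 1, 3 and 5 of Weeks 1-3 (Protocol 4.2.1.1), so the last is Day 14 + 5 = 19.
- Azacitidine is on Days 1-7, or Days 1-5 plus 8 and 9, of a 28-day cycle (Protocol 4.3.1.2).
- m is the number of later cycles with azacitidine only.
- Study treatment is taken to end with the last dose of the remaining component, and no new AML therapy starts.

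AE/TEAE window end = 19 + 30 = Day 49.

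SAE window end, Days 1-7 schedule = 28m + 7 + 30 = 28m + 37.

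Gap = 28m + 37 - 49 = 28m - 12 for m of 1 or more. On the 5-2-2 schedule it is 28m + 9 + 30 - 49 = 28m - 10. If the capsule stops on Day 1 of its cycle, the window closes on Day 31 and the Days 1-7 gap is 28m + 37 - 31 = 28m + 6.

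| Azacitidine-only cycles | Last capsule Day 19, AZA Days 1-7 | Last capsule Day 19, 5-2-2 | Last capsule Day 1, AZA Days 1-7 |
|---|---|---|---|
| 1 | 16 days | 18 days | 34 days |
| 2 | 44 days | 46 days | 62 days |
| 3 | 72 days | 74 days | 90 days |

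With the last capsule on Day 19 and no azacitidine-only cycle, both windows close on Day 49 and the gap is 0. Day 49 is Day 21 of the next cycle. The first azacitidine-only course on Days 1-7 (Days 29-35) is therefore covered, while a second, from Day 57, lies wholly outside.

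**How far this can be scaled up.** Mean gap per patient in an arm = share continuing azacitidine alone x gap. The documents give neither the share nor the number of cycles. Assuming shares of 3% to 25% and one to three cycles, the result runs from 0.03 x 16 = 0.5 days to 0.25 x 72 = 18 days. That range is too wide to support a single estimate.

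**New AML therapy.** Take an event 20 days after the last capsule, starting after new AML therapy has begun. Under SAP 6.4 it is a TEAE. Under SAP 9.2.1 and 9.2.2 it is post-treatment, and 9.2.1 adds a listing flag.

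**The case against.** The strongest reply is that azacitidine alone is not a state the plan describes. No passage says azacitidine may continue after the capsule is permanently stopped. Protocol 4.5 is a review rule, and SAP 6.3 may only be meant for partial cycles. Interruptions and drug holidays stop both drugs (Protocol 4.5 to 4.5.3). The Schedule places the End of Treatment visit 30 days after the last study drug intake, Protocol 5.2 times follow-up from the last study drug dose, and SAP 9.1 ends the treatment period at the last pracinostat/placebo dose. If the last capsule is the end of study treatment, the windows coincide. They also coincide if continued azacitidine counts as new AML therapy. SAP 7.8 exempts azacitidine only up to 3 days, although that is a censoring rule for time-to-event analyses.

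This stands as a limit: the gap is conditional. It does not remove the inconsistency. Permanent discontinuation of either component is written into Protocol 4.5, and the end of study treatment is undefined when one component stops. Under either rescue reading, serious events on later azacitidine would go uncollected as well.

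The safeguards are real but partial. Cycle visits ask for adverse events without an exception, SAP 9.2 lists all events whenever reported, deaths are summarised by cause, and laboratory shift tables use the worst value after baseline. None of these moves the 8.2 limit or the TEAE cut-off. SAP 9.2.1 shows which new-therapy rule was probably intended, but 6.4 still says otherwise.

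A reader might go further and infer that the active arm will look safer. The documents do not show this. The rule is identical in both arms, and bias needs unequal capsule-only stopping. Protocol 4.5 points both ways: it lists toxicities likely due to pracinostat, but starts reductions with azacitidine when attribution is unclear.

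**Conclusion.** The mismatch of anchors is certain on the text, and so is the conflict between SAP 6.4 and SAP 9.2.1/9.2.2. The loss of events is conditional on patients continuing azacitidine after permanently stopping the capsule. For such a patient, on the Days 1-7 schedule with a last capsule on Day 19, the gap is 16 days after one azacitidine-only cycle and 28 more for each further cycle. Otherwise it can be nil.

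A flat statement that toxicity is under-counted, or a percentage of treated time lost, would go beyond the documents because they give no number of such patients. The point concerns safety tables only. The overall survival test is unaffected. It should be corrected because the tables cannot be programmed unambiguously as the text stands.

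**What to change.** Leave the start points alone: adverse and serious event collection from consent, TEAEs from the first study-drug dose. Then:

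1. Reconcile Protocol 5.1.14, 8.1.1.5, 8.2, 8.2.1 and footnote U, and SAP 6.4, 9.2.1 and 9.2.2, on one end anchor: 30 days after the last dose of either component of study treatment, meaning the later of the two.
2. State how azacitidine-only cycles are handled and when study treatment counts as ended if one component stops. Which clinical rule applies is for the sponsor to state.
3. Use one new-AML-therapy rule, worded identically in SAP 6.4, 9.2.1 and 9.2.2.
4. Flag events starting more than 30 days after the last capsule, so that tables on the study-drug anchor can still be shown beside the wider ones.
5. Report the number of azacitidine-only patients by arm, which settles whether the gap matters.

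If adverse-event collection cannot be reopened, steps 3 to 5 and reclassifying the serious events already collected need only the SAP. The cost is wording in both documents and some extra event entry for azacitidine-only patients. If sites have already moved them to quarterly follow-up, that entry needs added contacts. The statistical downside is that later events mainly reflecting azacitidine enter the TEAE tables, which is why the flag is needed.
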